## **Abstract**

### **Introduction:**

Home blood pressure (BP) and unattended automated BP (uAOBP) monitoring have been suggested by guidelines in the care of hypertensive subjects. Moreover, BP measurements in the peripheral arteries cannot serve as direct substitutes for their central counterparts. However, comparative effectiveness and safety between BP-guided strategies using these BP measuring devices have never been evaluated.

### **Methods and analysis:**

Patients with uncontrolled or newly diagnosed hypertension aged 20-90 years will be recruited via outpatient clinics and allocated into three arms by stratified randomization (baseline systolic BP 130-155 mmHg and 155-180 mmHg): home BP, uAOBP, and central BP-guided treatment. Patients and physicians will be blinded to the allocated interventions by providing measured BP values in the clinic through a standardized report format. A common BP target with SBP 130 mmHg is adopted for these BP-guided strategies. The primary outcome is the change of 24 hour mean ambulatory SBP at 3 months. Key secondary outcome is to determine the proportions of achieving target BPs at 3 months and the decrease of left ventricular mass at 12 months.

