### **Study protocol**

Patients will be randomized to have hypertension management decisions made on the basis of the uAOBP, home BP, and central BP monitoring. Randomization will be done by using computer-generated randomization codes in 2 strata with baseline systolic BP (uAOBP) 130-155 mmHg and 155-180 mmHg. The BP measurements on left or right arm will also be determined by randomization codes.

To guide the management of hypertensive patients, medication adjustment will be made based on a published guideline with the measured BP through different BP monitoring methodologies. The use of different devices to obtain BP for guiding the care of hypertensive patients is aimed to determine whether these BP monitoring may be of comparable clinical value in routine practice. To achieve this, intervention patients will have medications titrated to normalize these different BP values. The target BP level, SBP 130 mmHg, of these different BP monitoring strategies are based on the latest guideline.

An overview of study protocol and acquired measures is presented in Table 1.

Although we encourage the adjustment of medication being adhered to the practice guideline, the choice of drug adjustment will be left to the discretion of the patient's attending doctor. During the measurement periods of home BP monitoring, no medication adjustment is allowable to preserve the comparability between different BP values. On the scheduled visits, the corresponding BP will be measured before meeting doctors and provided for clinicians to adjust patients' medication according to practice guideline. In summary, if the measured SBP is well within the target BP without possible side effects caused by antihypertensive agents, no medication adjustment is required. If the differences between measured SBP and target BP is less than 20 mmHg, the suggested maximal dose adjustment is 1 drug. If the BP differences are above 20 and 40 mmHg, addition of 2 drugs (or single pill combination) or 3 drugs (or single pill combination) are suggested, respectively. If low BP (less than 90/70mmHg) or any possible drug related side effects was noted, cautious adjustment of antihypertensive will be done. The dose adjustment and any possible side effects will be recorded throughout the whole study conduct period.

A sub-study will be performed to test the level of agreement between different measured BP values.

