#### **BP monitoring: uAOBP, central BP, and home BP**

Firstly, BP will be taken simultaneously from both upper arms by an oscillometric BP monitor (WatchBP Office Central; Microlife AG, Widnau, Switzerland). Subjects with SBP Differences between both arms more than 5 mmHg will be excluded. The performance of BP measurements will be adhered to the standard BP measurements procedures. For the uAOBP and CBP, the measurements will be conducted in a quiet room without the presence of clinical personnel. Patients will be seated in a quiet room without talking and taken as an average of 3 measurements with an automated device (HEM-907, Omron Healthcare, Lake Forest, IL) that has been preset to wait 5 minutes before measurements. Simultaneously, the central BP will be measured in the other upper arm. (WatchBP Office Central; Microlife AG, Widnau, Switzerland). The determination of the right or left upper arm for uAOBP or central BP will be made in a random order by computer generated random codes before the enrollment. As for the home BP measurements, a validated device (WatchBP Home; Microlife AG, Widnau, Switzerland) will be provided for all subjects allocated to the home BP arm to measure their BP at home. Subjects are requested to take BP in the morning (within 2 hours after awakening) and afternoon before meals for 7 consecutive days before the scheduled clinical visits. BP in the first day of the measurements will be discarded and an average of home BP (all BP reading and BP in the morning and in the afternoon) will be generated and provided

for clinicians to guide their treatment. The ambulatory BP of all subjects will be measured at baseline, at 3 months, and at the end of the study by a validated device (WatchBP O3 AFIB Ambulatory). Similarly, the choice of right or left arm for the measurement of ambulatory BP will be determined in a random manner. All the automated BP readings are stored digitally for analysis and corresponding BP values in each arm will be provided for clinicians to guide their hypertension management.

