### **Randomization, Outcomes, and Masking**

Each patient will be randomly assigned, using a standard computer protocol at the General Clinical Research Center, Taipei Veterans General Hospital, Taipei, Taiwan, to intervention in a 1:1:1 ratio using sealed opaque envelopes (sequentially numbered). The study coordinator will oversee the enrollment and intervention assignment and keep allocation concealment. The Primary outcome is the change of 24 hour mean ambulatory SBP at 3 months. The secondary outcomes include the change of 24 hour mean ambulatory DBP at 3 months, decrease of left ventricular mass at 12 months, change of SBP/DBP measured by uAOBP monitoring, home BP monitoring, or central BP monitoring, change of quality of Life, change of medication count and side effects. Any possible treatment related side effects including hypotension, injurious fall, dizziness, electrolyte imbalance (serum Na <130meq/L, serum K > 5.5 or <3.0 meq/L), syncope, acute renal failure (increase in serum

creatinine > 1.5 times baseline, or increase in serum creatinine by  $\geq 0.3$  mg/dL), and bradycardia (heart rate <50 bpm detected by electrocardiogram) will be recorded and evaluated. The medication quantity will be determined by daily defined dose (DDD) calculated as per World Health Organization standard (the DDD is a system for exact quantification of drug amount and standardization to enable comparison across drug classes, eg,  $1 \times \text{DDD} = 150$  mg irbesartan or 5 mg amlodipine). The quality of life is assessed by the Bulpitt hypertension- specific questionnaire. Two-dimensional echocardiography will be obtained by Artida Echocardiograph (Toshiba Medical Systems Corporation, Tokyo, Japan) and end-diastolic left ventricular (LV) dimensions were used to calculate LV mass by an anatomically validated formula, and subsequently normalized body height The caring physicians will remain blinded to the allocation by providing them with the measured BP values through a standardized report form without the knowledge of the used BP monitoring devices. Except patient reported outcome and adverse events, the investigators and participants are blinded to all the above outcome variables (which will be calculated at the end of the study), and assessment of LV mass will be conducted on side-by-side images by a technician blinded to allocation.

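### Target-BP attainment is called key secondary but is missing from the outcome list and has no stated measuring device; score all arms on one common measure

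*Combined protocol and SAP*

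**What the plan says.** All references are to the combined protocol and SAP.

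- **Abstract, Methods and analysis:** "Key secondary outcome is to determine the proportions of achieving target BPs at 3 months", together with left ventricular mass at 12 months. The same paragraph states: "A common BP target with SBP 130 mmHg is adopted for these BP-guided strategies".
- **Study protocol:** "The target BP level, SBP 130 mmHg, of these different BP monitoring strategies are based on the latest guideline", and "intervention patients will have medications titrated to normalize these different BP values". The 130 mmHg figure therefore appears as a titration target, applied to whichever measurement guides the arm.
- **Randomization, Outcomes, and Masking:** "The secondary outcomes include the change of 24 hour mean ambulatory DBP at 3 months, decrease of left ventricular mass at 12 months". The list continues with change in SBP/DBP by each of the three methods, quality of life, medication count and side effects. Target attainment is not on it.
- **Data Analysis and Statistical Analyses:** models are named for LV mass index, ambulatory BP, heart rate, quality of life, drug dose and medication recommendations. Attainment is not named, so only the general chi-square test for categorical variables would cover it.
- **BP monitoring:** "The ambulatory BP of all subjects will be measured at baseline, at 3 months, and at the end of the study". No ambulatory target is defined anywhere.
- **Home BP:** Table 1 ticks it at Visits 1 to 7 with no restriction by arm, while the BP monitoring section supplies the home device to the home BP arm.

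**The concern.** A key secondary outcome needs a measure, a cut-off rule and an analysis. This one has a time point and a number. Leaving the device open means that it could be chosen after the data are seen.

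The choice matters because the arms differ precisely in how BP is measured. If each arm is judged on its own device, one that reads low helps its arm twice. More patients appear below target at the same true pressure, and fewer patients have treatment stepped up, so true pressure stays higher. The reported proportion would then mix the effect of the strategy with the calibration of the device. It could point the opposite way to the primary outcome, which uses ambulatory BP in every arm.

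**Working it through.** **1. The plan's own figure.** No figure is given for attainment. The sample size inputs (SD 11, margin 5, power 80%, dropout 10%) supply the SD and the number evaluable. With one-sided alpha 0.025 (sidedness is not stated), n = 2 × [11 × (1.960 + 0.842) / 5]² = 75.98, so 76 per arm. Then 76 × 1.10 = 83.6, which rounds up to the plan's 84. I use 76 evaluable per arm below.

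**2. Ranking on a common measure and on own devices.** Inputs: SD 11 (plan); cut-off 130 mmHg (the plan's titration figure, used only as an example); arm means and offset b (assumptions). Own-device readings are given the same SD. Attainment = Φ((130 − mean reading) / SD). Arm A has a true mean of 128 and an unbiased device. Arm B is truly d mmHg worse, and its device reads b mmHg low.

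- A: Φ(2/11) = 57.2%.
- B, d = 3, common measure: Φ(−1/11) = 46.4%.
- B, d = 3, own device, b = 5: Φ(4/11) = 64.2%.

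A deficit of 10.8 points becomes an advantage of 7.0.

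| d | B, common measure | b | B, own device | Against A (57.2%) |
|---|---|---|---|---|
| 1 | 53.6% | 1 | 57.2% | tie |
| 1 | 53.6% | 2 | 60.7% | reversed |
| 3 | 46.4% | 2 | 53.6% | order kept |
| 3 | 46.4% | 3 | 57.2% | tie |
| 3 | 46.4% | 5 | 64.2% | reversed |
| 5 | 39.3% | 5 | 57.2% | tie |
| 5 | 39.3% | 8 | 67.5% | reversed |

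With equal SDs the order reverses only when b exceeds d. At b = 0 the two scores agree. For d = 3 and b = 5, an SD of 8 gives A 59.9% and B 45.0% (common) or 69.1% (own). An SD of 15 gives A 55.3% and B 47.3% or 60.5%.

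**3. Equal true means, offset only.** Both arms have a true mean of 130, so attainment is 50.0% in the unbiased arm and Φ(b/11) in the other. The chance of a nominal p < 0.05 is Φ([Δ − 1.96√(2p̄(1−p̄)/76)] / √([p₁(1−p₁) + p₂(1−p₂)]/76)), where Δ is the difference between the two proportions and p̄ is their mean.

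| b (mmHg) | Own-device attainment | Chance of p < 0.05 |
|---|---|---|
| 2 | 57.2% | 14% |
| 3 | 60.7% | 26% |
| 5 | 67.5% | 59% |
| 8 | 76.6% | 93% |

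**4. Letting the offset drive titration.** This is an illustrative model and all its inputs are assumed: starting SBP 145 (SD 11); reading noise SD 6; three titration visits; a fall of 5, 10 or 15 mmHg for readings from 130, 150 or 170 upward; 200,000 simulated patients per setting.

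| Device offset | True mean | Own device < 130 | 24-h SBP < 130 |
|---|---|---|---|
| 0 | 130.5 | 47.6% | 46.7% |
| −3 | 132.2 | 53.7% | 34.3% |
| −5 | 133.3 | 57.9% | 26.8% |
| −8 | 135.0 | 63.9% | 17.7% |

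The arm reading 5 low, compared with the unbiased arm, is 57.9 − 47.6 = 10.3 points ahead on own devices and 46.7 − 26.8 = 19.9 points behind on the common measure. The condition in step 2 is met because three visits turn only part of the offset into a true difference (133.3 − 130.5 = 2.8 mmHg, less than 5). At zero offset the two scores differ by 0.9 points because of reading noise, which would be the same in every arm with equal noise.

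**The case against.** **The plan never says own-device scoring.** A reader might infer that each arm will be scored on its own device and that attainment is therefore not comparable. The documents do not establish this. They set 130 mmHg as a titration target, not as a scoring rule. Table 1 schedules uAOBP and central BP at every visit without restriction by arm, so scoring each device across all arms would also fit the wording. This stands: the problem is conditional. Own-device scoring remains the natural reading, because the only target is tied to the guiding measurements and no ambulatory target exists.

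**Attainment would not rest on the titration readings themselves.** A reader might infer that it does. The Visit 4 reading is new, and treatment up to then was set on earlier visits. Only the device is shared. This stands too.

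**No offset is documented.** The Blood pressure threshold section reports comparable central and brachial values in a national survey. That supports a small offset for the central device, but it does not address home against uAOBP. The same section accepts that central BP is usually the lower, and the Introduction argues that peripheral values cannot replace central ones.

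**Small artefacts would seldom be significant.** With 76 per arm, the 95% half-width for a difference in proportions is about 1.96 × √(2 × 0.25/76) = 16 points. An artefact of 6 points would usually be lost in that. This is fair for small offsets, less so for 5 mmHg or more.

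**The outcome list may not be exhaustive, and a chi-square test is provided.** Perhaps, but the list runs down to medication count and side effects, so a key outcome should be there. The test does not settle what is being tested.

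**Conclusion.** The gap is real: a key secondary outcome is absent from the outcome list and has no stated device or specific analysis. The distortion is conditional. It needs own-device scoring, which is implied but not stated, and a systematic difference between devices, which the plan neither quantifies nor excludes. A reversed ranking is possible under those conditions, and nothing in the documents shows that it will happen. The sizes above depend on assumed offsets, titration effects and a common SD, and the distortion between arms vanishes at zero offset. The primary outcome is unaffected. This is a cheap improvement.

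**What to change.** - Add the outcome to the list in Randomization, Outcomes, and Masking, with its measure, time point, cut-off rule and contrasts.
- Score all arms on 24-hour ambulatory SBP at Visit 4, already scheduled for everyone, against a single analysis threshold that the sponsor fixes before unblinding. This threshold is for scoring only and does not alter the titration targets.
- Replace the unadjusted chi-square test for this outcome with a risk difference and 95% CI, adjusted for randomisation stratum and baseline ambulatory SBP.
- Report own-device attainment as descriptive only. Visit 4 uAOBP against the stated 130 mmHg could be a supporting analysis, with the caveat that uAOBP is itself the guiding device in one arm.
- Reconcile the BP monitoring section with Table 1 on whether home BP is measured in all arms.

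The cost is outcome and analysis wording, with no new measurements for the main analysis. The one downside is that the sponsor must name an ambulatory analysis threshold, which the plan does not now contain.

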### **Ethics and dissemination:**

The study will be initiated in June 2018 and results are expected in 2020. The will provide randomized controlled trial evidence to support future guideline recommendations for optimal BP monitoring devices.

## Introduction

Throughout middle and old age, blood pressure (BP) is strongly and directly related to vascular and all-cause mortality, and lowering high BP has been shown to associate with a substantial risk reduction of cardiovascular diseases. However, the traditional BP used for clinical practice, the office BP, is usually measured in a busy and hurry clinical environment, and interfered by the well-known confounding whitecoat effect. As such, unattended automated office BP monitoring (AOBP) has been proposed as an effective solution and further promoted by Canadian physicians. Nonetheless, out-of-office BP, home BP and ambulatory BP, remains the methodology of recommendation for the detection of whitecoat effect, and its prognostic value has been demonstrated to be superior to the traditional office BP. In previous systematic review and meta-analysis, home BP has been shown to be as good as ambulatory BP in predicting target organ damage and a better guiding strategy than conventional office BP. Home BP monitoring, with its ability to detect morning and masked hypertension and a better tolerability than ambulatory BP monitoring for long-term use, can therefore be considered as a strategy of choice to replace office BP monitoring for guiding hypertension management.

Moreover, BP measurements in the peripheral arteries cannot serve as direct substitutes for their central counterparts because of the long-recognized differences

of blood pressure (BP) waveforms  and values  between the central aorta and peripheral arterial system. Thus, if the decisions on medication adjustment are made solely based brachial BP, there could be a considerable risk of over- or undertreatment.

Considering that there are many better strategies for guiding hypertension management than traditional office BP, there is an apparent need for investigating their comparative effectiveness and safety in the management of hypertension. We hypothesized that home BP may be non-inferior to AOBP and central BP-guided intervention in reducing ambulatory BP and designed the present randomized controlled trial.

## **Method**

### **Study Design and rationale of the reference standard: invasively measured**

#### **CBP**

This is a 12-month, prospective, randomized trial. The study is scheduled to commence in June 2018. We estimate to enroll a total of 252 patients with 84 subjects allocated into 3 arms. Details of the sample size calculation is provided in the statistics section.

#### **Study Population**

Patients with hypertension will be recruited via outpatient clinics and advertisement and in our hospital. Inclusion criteria are as follows: 20 to 90 years of age; nonpregnant; receiving antihypertensive therapy for uncomplicated essential hypertension and taking  $\geq 1$  but  $\leq 2$  types antihypertensive drugs (to rule out complicated or resistant hypertension) or hypertension newly diagnosed by uAOBP ( $uAOBP > 130$  mmHg at screening visit). Exclusion criteria are as follows: Poor adherence to medication; unable to conduct self-measurement blood pressure; history of polycystic kidney disease; congestive heart failure (a recent assessment of left ventricular ejection fraction  $< 40\%$  prior to screening visit); chronic kidney disease with estimated glomerular filtration rate  $< 30$  mL/min/1.73m^2 (MDRD) at screening visit; a recent document of severely abnormal LV mass index ( $> 59$  g/m2.7

in women and >64 g/m^2.7 in men) prior to screening visit; secondary causes of hypertension; uncontrolled hypertension (uAOBP >180/100 mm Hg at screening visit); history of severe aortic valve disease; history of upper limb obstructive atherosclerosis; BP Differences more than 5 mmHg between both arms at screening visit.

### **Study protocol**

Patients will be randomized to have hypertension management decisions made on the basis of the uAOBP, home BP, and central BP monitoring. Randomization will be done by using computer-generated randomization codes in 2 strata with baseline systolic BP (uAOBP) 130-155 mmHg and 155-180 mmHg. The BP measurements on left or right arm will also be determined by randomization codes.

To guide the management of hypertensive patients, medication adjustment will be made based on a published guideline with the measured BP through different BP monitoring methodologies. The use of different devices to obtain BP for guiding the care of hypertensive patients is aimed to determine whether these BP monitoring may be of comparable clinical value in routine practice. To achieve this, intervention patients will have medications titrated to normalize these different BP values. The target BP level, SBP 130 mmHg, of these different BP monitoring strategies are based on the latest guideline.

An overview of study protocol and acquired measures is presented in Table 1.

Although we encourage the adjustment of medication being adhered to the practice guideline, the choice of drug adjustment will be left to the discretion of the patient's attending doctor. During the measurement periods of home BP monitoring, no medication adjustment is allowable to preserve the comparability between different BP values. On the scheduled visits, the corresponding BP will be measured before meeting doctors and provided for clinicians to adjust patients' medication according to practice guideline. In summary, if the measured SBP is well within the target BP without possible side effects caused by antihypertensive agents, no medication adjustment is required. If the differences between measured SBP and target BP is less than 20 mmHg, the suggested maximal dose adjustment is 1 drug. If the BP differences are above 20 and 40 mmHg, addition of 2 drugs (or single pill combination) or 3 drugs (or single pill combination) are suggested, respectively. If low BP (less than 90/70mmHg) or any possible drug related side effects was noted, cautious adjustment of antihypertensive will be done. The dose adjustment and any possible side effects will be recorded throughout the whole study conduct period.

A sub-study will be performed to test the level of agreement between different measured BP values.

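### The ban on medication changes during home BP measurement has no safety exception, so read literally it could hold back a dose reduction for up to 7 days

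*Combined protocol and SAP*

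**What the plan says.** The Study protocol section sets the rule: "During the measurement periods of home BP monitoring, no medication adjustment is allowable to preserve the comparability between different BP values". It is unqualified, and comparability is its only stated purpose.

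The section on BP monitoring fixes the length. Readings are taken "for 7 consecutive days before the scheduled clinical visits", and of the result it says "BP in the first day of the measurements will be discarded and an average of home BP" is then produced for the clinician. The same section says the home device "will be provided for all subjects allocated to the home BP arm to measure their BP at home". Table 1, however, marks home BP at Visits 1 to 7 without naming an arm.

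After the ban, the Study protocol section turns to visits: "On the scheduled visits, the corresponding BP will be measured before meeting doctors". It then summarises the titration steps and ends that summary with: "If low BP (less than 90/70mmHg) or any possible drug related side effects was noted, cautious adjustment of antihypertensive will be done". This last instruction carries no timing of its own. Two further statements matter for the remedy: "The dose adjustment and any possible side effects will be recorded throughout the whole study conduct period", and "A sub-study will be performed to test the level of agreement between different measured BP values".

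The sentence before the ban leaves the choice of drug adjustment to the attending doctor. The Data Safety Monitoring section has a Medical Safety Officer report safety issues to a board that meets twice a year.

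**The concern.** A rule written to protect a series of readings also covers, on its wording, dose reductions made for the patient's safety. The situation is narrow. Nothing in the plan has clinicians looking at home readings before the visit, so it arises mainly when a patient contacts the clinic during a measurement week with dizziness, a fall or symptoms of hypotension. Such symptoms are foreseeable: the trial admits patients up to age 90, and the titration guide suggests adding two or three drugs when systolic BP is more than 20 or 40 mmHg above target.

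At stake is a short delay for a small number of patients. In addition, a physician who sensibly reduces a dose during the week would depart from the protocol's literal wording.

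**Working it through.** The plan gives no figure on this point, so there is none to reproduce. The check is a reading of the text followed by a count of days.

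**Text**
- Ban: applies during home measurement; no exception; no reference to the low-BP instruction.
- Low-BP instruction: last item of the visit summary; no reference to the ban.
- Doctor's discretion: covers the choice of adjustment; not said to override the ban.
- Safety board and Medical Safety Officer: a reporting line, with no rule for one patient's dose within a week.
- Table 1 and the outcomes section: no unscheduled-visit or rescue rule.

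**Inputs from the documents**
- Period: 7 days before a visit (BP monitoring section).
- Visits after randomisation: days 30, 60, 90, 180, 270 and 360 (Table 1), so 6 periods, 3 of them in the first 90 days.
- Patients: 84 per arm, 252 in all, before dropout.

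**Time under the ban, per patient taking home series**
- Whole study: 6 × 7 = 42 days; 42/360 = 11.7%.
- First 90 days: 3 × 7 = 21 days; 21/90 = 23.3%.
- Patient-days: 84 × 42 = 3,528 (home arm) or 252 × 42 = 10,584 (all arms).

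**Longest delay**
A problem on day d of the period waits 7 − (d − 1) days: 7 days for day 1, 1 day for day 7. With reports spread evenly, the mean is 3.5 days in continuous time, or 4 counting whole days.

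**Events inside a period**
Assumed rate: 5 to 20 events needing a dose change per 100 patients over 360 days. Expected number = patients × rate × share of time under the ban.

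| Timing assumed | Home arm (84) | All arms (252) |
|---|---|---|
| Even over 360 days, 5 per 100 | 84 × 0.05 × 42/360 = 0.49 | 252 × 0.05 × 42/360 = 1.47 |
| Even over 360 days, 20 per 100 | 84 × 0.20 × 42/360 = 1.96 | 252 × 0.20 × 42/360 = 5.88 |
| All in first 90 days, 5 per 100 | 84 × 0.05 × 21/90 = 0.98 | 252 × 0.05 × 21/90 = 2.94 |
| All in first 90 days, 20 per 100 | 84 × 0.20 × 21/90 = 3.92 | 252 × 0.20 × 21/90 = 11.76 |
| All within 23 days of a visit | 0 | 0 |

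The last row holds at nominal timing, because a period opens no sooner than 30 − 7 = 23 days after the previous visit.

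**What allowing the change does to the home average**
Day 1 is dropped and days 2 to 7 are averaged. A change on day d leaves 7 − d of the 6 averaged days on the new dose: 6, 5, 4, 3, 2, 1, 0 for d = 1 to 7, mean 21/7 = 3 of 6. If a dose cut raised systolic BP at once by 5 to 10 mmHg (assumed), an affected average would shift by 2.5 to 5 mmHg on average and by 5 to 10 mmHg at most.

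**The case against.** The strongest reply is that there is no conflict. The paragraph runs in order: no changes while readings are collected, then the visit, then what to do at the visit. On that sequence the rules follow one another, and a reader who inferred two contradictory rules would be going too far. This stands, and it is the more natural reading. It does not supply an exception, however: if the low-BP instruction belongs to the visit, nothing expressly permits a safety change in the week before. If that instruction is instead taken to apply at any time, it already directs action, but the text does not say so.

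A second reply is masking. Treating physicians are not told which BP method is in use. If only the home arm takes home series, a physician called during the week may not know that the ban applies, and literal application becomes less likely. That also stands and lowers the practical risk. It equally means the physician cannot tell whether acting breaches the protocol.

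A third is that any sensible doctor would act. Probably so; the less certain cases are dizziness and mild hypotension.

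A reader might also infer that different sites would act differently. The documents do not support this: recruitment is at one hospital, and no second site is named. At most, physicians might differ.

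**Conclusion.** The point holds as a missing safety exception and is minor. The text of the ban, its single purpose and the lack of any exception are clear from the documents. So is the 7-day upper limit on delay at nominal timing.

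The number of events is much less certain. It rests on assumed rates and timing, and on who takes home series, which the BP monitoring section and Table 1 leave open: 0 to 3.9 events in the home arm, or 0 to 11.8 if all arms do. Few events are likely on either reading.

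Two stronger conclusions are tempting and unsupported. One is that the ban biases the 3-month ambulatory systolic comparison; no scheduled titration is lost, and nothing in the plan shows such an effect. The other is that clinicians would withhold a reduction after a serious event such as syncope; the documents give no ground for expecting that.

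**What to change.** Limit the ban to titration toward the BP target. State that adjustment for low BP or a suspected side effect is allowed at any time, in any arm, and takes precedence over the ban. Wording that applies to every arm works without revealing allocation.

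Record the date of such a change, so that the affected home series can be identified and, if wished, left out of the agreement sub-study. Dose adjustments are already recorded, so this adds little. Keep the scheduled visit and the ambulatory recording on time.

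Two additions are optional: a line on the standard report form, identical in every arm, saying whether medication changed in the past 7 days; and a statement that an interrupted series is not repeated if that would move the visit outside its ±7-day window.

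The cost is about two protocol sentences and a few home averages that are less comparable. Sample size and the primary analysis do not change. It would also help to state whether home series are taken in one arm or in all.
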